8.1.3.2 Per Protocol Analyses

Per Protocol analysis will be performed using the Per Protocol Sample.

8.1.3.3 Sensitivity Analyses for Violation of Normality Assumption

The primary endpoint MMRM analysis is a maximum likelihood method that relies on normality assumption. Residual analyses will be carried out to examine model assumption.

In the case of gross violations of the normality assumptions, nonparametric van Elteren test⁸ (van Elteren, 1960) will be performed to compare treatment effect at Week 14 on both LOCF

SAP 405-201-00013

dataset and Multiple Imputation (MI) data. The van Elteren test is a generalized CMH procedure useful for stratified continuous data in non-normal setting. It belongs to a general family of Mantel-Haenszel mean score tests. The test is performed via SAS procedure PROC FREQ, by including CMH2 and SCORES=MODRIDIT options in the TABLE statement. The stratification factor is trial center.

In addition, other methods that are robust to distributional assumption will also be performed to provide different views on the primary efficacy result, these include generalized estimating equations (GEE), weighted GEE (WGEE), and MI-robust regression⁹.

For MI-van Elteren test and MI-robust regression, imputation datasets will be generated with SAS MI procedure, each dataset will be analyzed, then an overall estimate is derived with SAS MIANALYZE procedure.

8.1.4 Subgroup Analyses

Subgroup analyses of change from baseline of the double-blind treatment period in AISRS total score to every scheduled visit in the double-blind treatment period will be performed by the following factors:

- Sex (Based on the biological status)
- Race (White and All Other Races)

All subgroup analyses will be conducted using the same MMRM analysis as for the primary efficacy analysis except that the fixed class effect term for trial center will not be included in the model.

Interaction effects of treatment-by-subgroup will be assessed at Day 42 for the subgroups identified in the previous paragraph. MMRM analyses will be performed by adding addition of terms for subgroup-by-day and treatment-by-subgroup-by-day. These treatment-by-subgroup interaction analyses will be presented in statistical documentation.

8.2 Key Secondary Efficacy Endpoint

The key secondary efficacy endpoint is the change from baseline of the double-blind treatment period to Day 42 using the CGI-S. This key secondary efficacy endpoint will be analyzed by fitting the same MMRM model described in the primary analysis.

To control the overall experiment-wise type I error at 0.05 level, A fixed sequence testing approach will be applied. The statistical test will be performed in the following order:

- 1) Change from baseline to Day 42 in the double-blind treatment period in AISRS total score between centanafadine 400 mg TDD and placebo;

SAP 405-201-00013

- 2) Change from baseline to Day 42 in the double-blind treatment period in AISRS total score between centanafadine 200 mg TDD and placebo;
- 3) Change from baseline to Day 42 in CGI-S score between centanafadine 400 mg TDD and placebo;
- 4) Change from baseline to Day 42 in CGI-S score between centanafadine 200 mg TDD and placebo.

The testing procedure will stop at the first comparison where the p-value is ≥ 0.05 . None of the subsequent comparisons will be performed.

8.3 Other Efficacy Endpoints

Other efficacy analyses are listed below. All other efficacy variables will be evaluated at a nominal 0.05 level (2-sided) without adjusting for multiplicity.

- 1) Change from baseline in AISRS total score for every scheduled visit during the double-blind treatment period other than the Day 42 visit;
- 2) Change from baseline for the Inattentive subscale and Hyperactive-Impulsive subscale of the AISRS for scheduled visits during the double-blind treatment period, separately at every visit
- 3) Change from baseline in CGI-S for every scheduled visit during the double-blind treatment period other than the Day 42 visit
- 4) CGI Change from Baseline will be collected at each scheduled visit
- 5) Percentage of responders at each post-baseline visit during the double-blind treatment period, where a responder is defined as a subject with a CGI Change from Baseline score of 1 or 2 OR a $\geq 30\%$ improvement in ADHD symptoms compared with baseline as measured by the AISRS total score
- 6) Response rate at each post-baseline visit during the double-blind treatment period, where response is defined as
 - a) a CGI Change from Baseline score of 1 or 2 OR a $\geq 20\%$ improvement in ADHD symptoms compared with baseline as measured by the AISRS total score.
 - b) a CGI Change from Baseline score of 1 or 2 OR a $\geq 40\%$ improvement in ADHD symptoms compared with baseline as measured by the AISRS total score.
- 7) Remission rate for every scheduled visit during the double-blind treatment period, where remission is defined as AISRS total score ≤ 18 .

Variable (1) through variable (3) will be evaluated using the same MMRM model described in the primary analysis. Variable (4) will be evaluated by the Cochran Mantel Haenszel (CMH) Row Mean Score Differ Test controlling, in LOCF analysis, for trial center. Variable (5) through variable (7) will be evaluated by the CMH General Association Test controlling, in LOCF analysis, for study center. An OC analysis will also be conducted for variables (4)

SAP 405-201-00013

through (7) but will not control for trial center. Separate summary and statistical test for response rate based only on the AISRS improvement and only on the CGI Change from Baseline score will be presented for (5) and (6).

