1.	Subjects with a current primary DSM-5 diagnosis of ADHD (including predominantly inattentive presentation, hyperactive presentation, or combined presentations) as confirmed by the ACDS Version 1.2.
2.	Subjects who are not receiving any pharmacological treatment for ADHD must have an AISRS score of ≥ 28 at screening. Subjects who are receiving pharmacological treatment for ADHD at screening must have a minimum AISRS score of ≥ 22 at screening.
3.	Subject is 18 to 55 years of age, inclusive, at the time of consent.
4.	Subject has a BMI of 18 to 40, inclusive.
5.	Subject is able to swallow multiple tablets.
6.	Subject is willing and able to comply with all testing and requirements as defined in this protocol.
7.	Subject is able to provide electronic informed consent to participate in the trial in accordance with the ICH GCP Guidance E6 and applicable regulations before completing any trial-related procedures.
8.	Subject is willing to discontinue all prohibited psychotropic medications (Section 4) starting from the time of signing the informed consent and up to the 7-day follow-up period. Subjects that do not rollover into Trial 405-201-00015 must be willing to discontinue all prohibited psychotropic medications starting from the time of signing the informed consent until after the follow-up telephone call 10 days after the last dose of IMP.
9.	Subject is able to read English or Spanish well enough to understand the nature of the trial and to read and understand the written word in order to complete subject-reported outcome measures and be able to communicate effectively to be reliably rated on assessment scales; must be able and agree to comply with all protocol requirements, including the prescribed dosage regimens, discontinuation of prohibited medications, and report for regularly scheduled office visits.
Inclusion Criteria Assessed at Baseline	
10.	Subjects who were not receiving any pharmacological treatment for ADHD at screening must have an AISRS score of ≥ 28 at baseline. Subjects who were receiving pharmacological treatment for ADHD at screening must also have a minimum AISRS score of ≥ 28 at baseline.
11.	Subject must have a CGI-S score of ≥ 4 (\geq moderate impairment) at baseline.

BMI = body mass index; CGI-S = Clinical Global Impression-Severity of Illness Scale.

Protocol 405-201-00013

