The primary efficacy endpoint is the change from baseline at Day 42 in Adult ADHD Investigator Symptom Rating Scale (AISRS) total score. The trial will compare the placebo arm to the centanafadine dose arms, randomized at a ratio of 1:1:1, with an overall alpha of 0.05 for the primary endpoint.

Based on the results from Phase 2 centanafadine trials, it is reasonable to expect a treatment effect of 5 points with a standard deviation (SD) of 12.5 in the mean change from baseline to Day 42 on AISRS total score. The planned sample size of 405 evaluable subjects (135 in each treatment arm) will yield at least 90% power to detect the treatment effects at a 2-tailed significance level of 0.05.

A sufficient number of subjects will be enrolled and randomized to achieve approximately 405 evaluable subjects in the Double-blind Treatment Phase (i.e., subjects with an AISRS total score at baseline and at least 1 subsequent AISRS total score in the Double-blind Treatment Phase). After allowance of 10% non-evaluable subjects in the Double-blind Treatment Phase, the total number of subjects to be randomized is 450 (150 in each treatment arm). In order to ensure 405 evaluable subjects, the number of non-evaluable subjects will be monitored in a blinded manner on an ongoing basis During the trial. The power and sample size were obtained using the PASS 14 (2015) statistical computing software.

5 Data Sets for Analysis and Missing Data

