In this hypothetical strategy, the event of withdrawing IMP is considered missing at random (MAR), and the primary endpoint of the trial could be considered as a combination of the responses of on-treatment completers at Day 42 and the imputation of the endpoint to Day 42 following the trend in each treatment group using the MMRM method for subjects who withdraw IMP during the trial. All data collected during the trial treatment period will be used for statistical analysis. For the primary efficacy analysis, the treatment effect will be estimated using the MMRM method described below. Under the MAR assumption, MMRM provides an unbiased estimate of treatment effect for the treatment period. Analyses with missing values imputed by multiple imputation under MNAR and other methods will be performed as sensitivity analyses. The primary analysis will be performed on Efficacy Sample which includes all randomized subjects who took at least 1 dose of IMP in the double-blind treatment period and who have both a baseline for the double-blind treatment period and at least one post-randomization AISRS total score during the double-blind treatment period. The primary efficacy analysis will be performed by fitting a MMRM analysis with an unstructured (UN) variance covariance structure in which the change from baseline for the double-blind

SAP 405-201-00013

treatment period in AISRS total score at the scheduled double-blind treatment period visits will be the dependent variable based on the OC data set. The model will include fixed class effect terms for treatment, study center, visit day, and an interaction term of treatment by visit day. The model will also include the interaction term of baseline values for the double-blind treatment period of AISRS Total score by visit day as covariates. The primary comparison between centanafadine (400 mg TDD group or 200 mg TDD group) and placebo at Day 42 in the double-blind treatment period will be estimated as the difference between Least Squares (LS) means utilizing the computing software SAS procedure PROC MIXED.

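### Remission (AISRS total 18 or less) is tested without baseline AISRS, a strong predictor of it, so a modest amount of precision is given away

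*SAP*

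**What the plan says.** SAP 8.3 (Other Efficacy Endpoints) lists the 30% responder rate (5), the 20% and 40% response rates (6) and the remission rate (7), for scheduled visits in the double-blind period. For remission the wording is "where remission is defined as AISRS total score ≤ 18". The test is given as: "Variable (5) through variable (7) will be evaluated by the CMH General Association Test controlling, in LOCF analysis, for study center". The OC analysis of the same variables drops centre, so it has no covariate at all. SAP 8.3 names a test but no adjusted difference or confidence interval for these endpoints, and neither document plans a baseline-adjusted analysis of remission elsewhere.

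By contrast, the primary MMRM of AISRS change carries baseline (SAP 8.1.1): "The model will also include the interaction term of baseline values for the double-blind treatment period of AISRS Total score by visit day as covariates". Both ANCOVAs (LOCF and OC, SAP 5.2 and 8.1.3.1) also include it.

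The entry rule (Protocol Table 3.4.2-1, criterion 10) sets the lower end of the baseline range: subjects "must have an AISRS score of ≥ 28 at baseline". The scale maximum is 54.

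**The concern.** Remission is a fixed cut on the raw score, so its difficulty depends on where a subject starts. From a baseline of 28 the subject must fall 28 − 18 = 10 points (36%). From 54 the fall is 54 − 18 = 36 points (67%). A covariate that orders subjects this clearly is left out of the test, although it is already in the database and in the SAP's models for the same scale.

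Two things are at stake. The comparison is less precise than the collected data allow. And if the arms differ in baseline severity by chance, the remission difference moves with it and nothing in the analysis removes that shift.

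**Working it through.** **The plan's own figure.** SAP section 4 assumes "it is reasonable to expect a treatment effect of 5 points with a standard deviation (SD) of 12.5" with 135 evaluable per arm. SE = 12.5 × √(2/135) = 1.521. Power = Φ(5/1.521 − 1.96) = Φ(1.326) = 0.908, which reproduces the stated 90% or more. 405/0.90 = 450 also reproduces. No power is stated for remission.

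**Inputs for sizing the omission.** These come from the output appended to the SAP and are used only to gauge magnitude.
- Baseline AISRS: means 39.60, 39.56 and 39.53; SDs 6.69, 6.82 and 7.20 (STAT-4.3); pooled SD 6.90.
- Slope of Day 42 change on baseline, model without centre: baseline Type III SS 1255.84; within-arm sum of squares 146 × 6.694² + 146 × 6.817² + 143 × 7.198² ≈ 20,735; √(1255.84/20,735) = 0.246, sign taken as negative. Residual SD 10.696.
- Slope from the MMRM (STAT-4.1.1): −0.1177 (SE 0.0857). Residual variance 117.05, so SD 10.82.
- Mean placebo change at Day 42: −7.46 (STAT-4.3) or −6.98 (MMRM).

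**Remission probability by baseline.** With baseline b, mean change m, slope β and residual SD σ:

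P(b) = Φ((18.5 − [b + m + β(b − 39.56)]) / σ)

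For placebo with m = −7.46, β = −0.246 and b = 28, the fitted score is 28 − 7.46 + 2.84 = 23.38, and Φ((18.5 − 23.38)/10.696) = Φ(−0.456) = 0.324.

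| Baseline | Fall needed | β = −0.246 | β = −0.118 |
|---|---|---|---|
| 28 | 10 | 0.324 | 0.377 |
| 33 | 15 | 0.209 | 0.235 |
| 40 | 22 | 0.096 | 0.098 |
| 46 | 28 | 0.042 | 0.037 |
| 54 | 36 | 0.011 | 0.007 |

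The AUC of baseline for remission is 0.73-0.75. Baseline explains 7-9% of the variance of remission status.

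**Effect on the test.** 6,000 simulated comparisons per row; 147 versus 144 subjects in the 38 pooled-centre sizes of STAT-4.5.1; no centre effect; baseline a truncated normal on 28-54 (an assumption). The residual SD of 12.3 is a sensitivity value near the planned SD.

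| Effect (points) | β | σ | CMH by centre | CMH, no strata | Logistic + baseline | Variance cut in risk difference |
|---|---|---|---|---|---|---|
| 0 | −0.246 | 10.7 | 0.047 | 0.048 | 0.048 | 5.3% |
| 5 | −0.246 | 10.7 | 0.670 | 0.679 | 0.716 | 7.4% |
| 5 | −0.246 | 12.3 | 0.600 | 0.612 | 0.638 | 7.3% |
| 2.4 | −0.246 | 10.7 | 0.197 | 0.202 | 0.212 | 7.0% |
| 2.74 | −0.118 | 10.8 | 0.228 | 0.229 | 0.242 | 10.0% |

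At the 5-point effect with the MMRM slope, repeat runs gave power of about 0.656 unadjusted and 0.70-0.71 adjusted. One had SDs of the risk difference of 0.0443 and 0.0418: 1 − (0.0418/0.0443)² = 11%. Across runs the variance cut is about 5-12%. Roughly 1 point of the gain over CMH by centre comes from dropping the many small strata, not from baseline.

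**Chance imbalance.** The SE of a baseline difference is 6.904 × √(1/147 + 1/144) = 0.81 points. Raising baseline by one point lowers placebo remission by 1.25 percentage points (β = −0.246, m = −7.46) or 1.41 (β = −0.118, m = −6.98). A one-SE imbalance therefore shifts remission by 0.81 × 1.25 = 1.0 to 0.81 × 1.41 = 1.1 percentage points. The expected difference at a 5-point effect is about 10.8 (0.230 − 0.122).

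**Response, for comparison.** For the 30% AISRS criterion, adding baseline changes the variance by −0.4% to +0.1% in the same simulations, and power by almost nothing (0.877 for CMH by centre, 0.880 adjusted, at 5 points). The AUC is 0.52-0.55.

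**The case against.** The strongest reply is that nothing is invalid. Under randomisation the CMH test holds its level (0.047 above), and a chance imbalance is not bias. Remission is tested at a nominal 0.05 without multiplicity control, sits outside the fixed sequence of SAP 8.2, and is absent from the endpoints in Protocol 7.3.2.2. The same score already has baseline-adjusted inference in the primary MMRM. In the event the arms were nearly identical at baseline: differences from placebo of 0.03 and 0.06 points, worth less than 0.1 percentage point of remission. At an effect near 2.7, adjustment adds only 1-3 points of power.

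All of that stands and makes the point minor. It does not remove it. A plan is fixed before the baseline balance is known, and the precision gain does not need an imbalance.

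A reader might also infer that the response rates share the problem. The documents do not support that. Variables (5) and (6) are percentage improvements from the subject's own baseline, or a CGI change score of 1 or 2, so they are already scaled to baseline. The CGI part could not be modelled.

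Nor is remission the only AISRS test without baseline. The van Elteren test in SAP 8.1.3.3 stratifies by centre alone.

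**Conclusion.** The point holds for remission only, as a matter of precision. Adjusting for baseline AISRS would cut the variance of the remission risk difference by about 5-12%. It would add about 4-5 points of power at the planned 5-point effect (about 0.66 to 0.70), and about 1-3 points near 2.7. It would also remove about 1 percentage point of chance shift per one-SE baseline imbalance.

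Two stronger readings should be avoided. One is that baseline largely decides who remits: it is a strong predictor, but it explains under 10% of the variance of remission status. The other is that the CMH result is biased or has the wrong type I error; it does not.

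The sizes rest on a linear model with normal residuals and no centre effect, on an assumed baseline shape, and on slopes of −0.118 to −0.246. The Day 42 residuals are in fact skewed (−0.80 in STAT-4.9). The slope, residual spread and baseline distribution come from output run after the SAP was signed, so they gauge the omission and could not have been planning inputs.

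**What to change.** In SAP 8.3, for variable (7) only, add a logistic regression with treatment and baseline AISRS total, each dose versus placebo, in both the LOCF and OC analyses. Report the baseline-standardised difference in remission proportions with a 95% CI. Keep the CMH test as supportive, and leave variables (5) and (6) as they are.

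A conditional logistic model stratified by the 38 pooled centres is not recommended on this evidence. Several of those centres have one subject per arm, its gain was not checked, and it does not by itself give a standardised difference.

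The cost is a sentence or two of SAP text and a few lines of code, with no new data. The odds ratio will be conditional on baseline, which is why the standardised difference should be reported with it.

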8.4 Exploratory Efficacy Endpoints

The exploratory efficacy endpoints are listed below. The exploratory efficacy endpoints, when applicable, will be evaluated at a nominal 0.05 level (2-sided) without adjusting for multiplicity.

- 1) Change from baseline for Question 1 (Global Quality of Life) and Questions 9Aa – 9Ai and 9Ba – 9Bi (Impact of Symptoms) of AIM-A at scheduled visits during the double-blind treatment period, separately at every visit
- 2) Proportion of subjects in each response for the following questions of AIM-A at scheduled visits during the double-blind treatment period, separately at every visit
 - a. Questions 2-4 (Global Quality of Life)
 - b. Questions 5a-5j (Living with ADHD)
 - c. Questions 6a-6k (General Well-Being)
 - d. Questions 7a-7j (Work, Home and School Performance and Daily Functioning)
 - e. Questions 8a-8h (Relationships and Communication)
 - f. Economic impact (5 items)
 - g. Questions 17-23 (Demographics/Medication Status)
- 3) Change from baseline in the total score of (18 item) ADHD Symptoms score of the ASRS and subscale scores for ASRS at scheduled visits during the double-blind treatment period, separately at every visit

Variables (1) and (3) will be evaluated using the same MMRM model described in the primary analysis. Variable (2) will be summarized by descriptive statistics and no statistical comparisons between centanafadine and placebo will be performed.

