3.5.3 Exploratory Endpoints

The exploratory endpoints are the change from baseline to Day 28 and Day 42 in the ADHD Impact Module - Adult (AIM-A) and the Adult ADHD Self Report Scale (ASRS) total score and subscale scores.

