3.7.3.3 Attention-deficit/Hyperactivity Disorder Impact Module - Adult

The AIM-A (Table 3.7-1) is a subject self-report questionnaire which assesses quality of life in adults with ADHD. The questionnaire has 4 global quality of life items, 5 economic impact items, and 5 multi-item scales that assess the following key concepts: Living with ADHD, General Well-Being, Work, Home and School Performance and Daily Functioning. Additionally, Relationships and Communication, and Impact of Symptoms are also included.³⁴

Protocol 405-201-00013

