10.3.4 Attention-Deficit Hyperactivity Disorder Impact Module – Adult (AIM-A)

The AIM-A is a subject self-report questionnaire which assesses quality of life in adults with ADHD. The questionnaire has 4 global quality of life items, 5 economic impact items, and 5 multi-item scales that assess the following key concepts: Living with ADHD, General Well-Being, Work, Home and School Performance and Daily Functioning. Additionally, Relationships and Communication, and Impact of Symptoms are also included.

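### SAP 8.4 narrows the protocol's AIM-A change endpoint to Question 1 and Impact of Symptoms without giving a reason, leaving four of the five scales with no prespecified change or treatment contrast

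*SAP*

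**What the plan says.** Protocol 3.5.3 defines the endpoint without restricting it to particular questions: "The exploratory endpoints are the change from baseline to Day 28 and Day 42 in the ADHD Impact Module - Adult (AIM-A") together with the ASRS scores. The protocol synopsis repeats this. Protocol 7.3.3 leaves the statistical analysis of the exploratory endpoints to the SAP.

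Protocol 3.7.3.3 describes the questionnaire as four global items, five economic items and "5 multi-item scales that assess the following key concepts: Living with ADHD, General Well-Being, Work, Home and School Performance and Daily Functioning". It then adds: "Additionally, Relationships and Communication, and Impact of Symptoms are also included". SAP 10.3.4 repeats the description.

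SAP 8.4 splits the instrument in two.

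- Variable (1) is "Change from baseline for Question 1 (Global Quality of Life) and Questions 9Aa – 9Ai and 9Ba – 9Bi (Impact of Symptoms) of AIM-A", analysed with the primary MMRM.
- Variable (2) is "Proportion of subjects in each response for the following questions of AIM-A at scheduled visits during the double-blind treatment period". It covers Questions 2-4, 5a-5j, 6a-6k, 7a-7j and 8a-8h, the economic items, and Questions 17-23. For these, "Variable (2) will be summarized by descriptive statistics and no statistical comparisons between centanafadine and placebo will be performed".

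Protocol Table 3.7-1 schedules the AIM-A at Day -7, baseline, Day 28 and Day 42/ET.

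**The concern.** The distribution of answers at a visit is not a change from baseline. For four scales the SAP therefore replaces the variable that the protocol names with a different one, and it also rules out a comparison with placebo. Protocol 7.3.3 hands over the method of analysis; the endpoint itself is set in Protocol 3.5.3.

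At stake is what the trial can say about quality of life, which both documents give as the purpose of the AIM-A. The data needed for change on every scale will be collected. Without a prespecified score and model, any later result on these four scales would rest on scoring and analysis choices made after the plan was fixed.

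**Working it through.** No sample-size or error-rate formula applies. The check is a count of scales and items, set against the planned analysis.

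**Number of scales.** Protocol 3.7.3.3 gives five. Three are named in the first sentence and two in the next: 3 + 2 = 5, which reproduces the stated figure. SAP 8.4 attaches the same five names to Questions 5, 6, 7, 8 and 9.

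**Sorting by planned analysis.** Item counts follow from the letter ranges in SAP 8.4.

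| Scale | Questions | Items | Planned in SAP 8.4 |
|---|---|---|---|
| Living with ADHD | 5a-5j | 10 | Proportions, no comparison |
| General Well-Being | 6a-6k | 11 | Proportions, no comparison |
| Performance and Daily Functioning | 7a-7j | 10 | Proportions, no comparison |
| Relationships and Communication | 8a-8h | 8 | Proportions, no comparison |
| Impact of Symptoms | 9Aa-9Ai, 9Ba-9Bi | 9 + 9 = 18 | Change from baseline, MMRM |

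Items with proportions only: 10 + 11 + 10 + 8 = 39. All scale items: 39 + 18 = 57. Share: 39 / 57 = 68%. Three of the four global items (Questions 2-4) and the five economic items are also reported as proportions only.

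**Is there a score to analyse?** SAP 10.3 is the section for scoring and missing-data rules. Its AISRS part (10.3.1) and ASRS part (10.3.5) say how to form subscale scores and what to do with one missing item. The AIM-A part (10.3.4) describes the questionnaire and stops: it gives no scale score, item direction or missing-item rule.

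**Does the table list supply what 8.4 omits?** CT-5.7.1 to CT-5.7.4 are titled as mean change in the AIM-A and name no question or scale. CT-5.7.5 is the proportions table. These match variables (1) and (2) in turn. Where the SAP plans subscale analyses it lists them by name, as with the AISRS subscales (CT-5.3.x) and the ASRS subscales (CT-5.9.x). No AIM-A scale has such a table.

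**Size of the addition.** 4 scales x 2 post-baseline visits x 2 doses against placebo = 16 estimates.

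**The case against.** The best defence is that the endpoint is exploratory, its analysis is delegated to the SAP, and the protocol never promises a test for each AIM-A scale. Descriptive reporting of unadjusted exploratory outcomes is a legitimate choice, and proportions in randomised groups can still be compared by eye. The split between Questions 1 and 9 and the rest might reflect different response formats, which neither document describes. The mean-change tables show that some AIM-A change analysis is planned.

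Much of this stands as a limit on the point. A deliberate choice cannot be excluded, but the SAP states none. Generic table titles do not override the explicit allocation in SAP 8.4.

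Several stronger readings are tempting and are not supported:

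- A reader might infer that change on these scales cannot be reported at all. It could be derived post hoc, because the AIM-A is collected at baseline, Day 28 and Day 42. What is missing is prespecification.
- A reader might multiply 39 items by 2 visits and expect 78 frequency tables. Those would be blocks within one planned table, CT-5.7.5.
- A reader might argue that single items are unreliable. Neither document gives reliability data for the AIM-A, and the point does not need that argument.
- A reader might take Question 9 to be analysed item by item. SAP 8.4 does not say whether it is handled as items or as a score.

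**Conclusion.** The point holds as a minor one. SAP 8.4 narrows the protocol's AIM-A endpoint to Question 1 and Impact of Symptoms, gives no reason, and leaves four of five scales (39 of 57 scale items) with no prespecified change from baseline and no treatment contrast.

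This rests on reading the two scales named in the second sentence of Protocol 3.7.3.3 as the fourth and fifth of the five, which the question headings in SAP 8.4 support. It also assumes that the four scales can be scored. The documents do not give the scoring, so that has to be confirmed from the instrument.

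The AIM-A lies outside the fixed-sequence tests in SAP 8.2, so the primary and key secondary conclusions are unaffected.

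**What to change.** 1. In SAP 10.3.4, add scale scores and a missing-item rule taken from the instrument's scoring manual. State there whether Question 9 is analysed as a score or item by item.
2. In SAP 8.4, analyse change from baseline to Day 28 and Day 42 in the four scale scores with the MMRM already applied to variables (1) and (3), at the nominal 0.05 level. Keep the item proportions as supportive.
3. Name the scores or questions covered in the titles of CT-5.7.1 to CT-5.7.4.

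If the narrowing was intended, the SAP should at least say so and justify it against Protocol 3.5.3.

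The cost is SAP wording, a scoring program, a few tables, and 16 further exploratory estimates without multiplicity adjustment, to be read accordingly. No new data are needed. The SAP file already carries output dated 18 June 2020, after the April 2020 approvals. Scale results added after unblinding should be labelled post hoc.
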